4. SUBJECT ELIGIBILITY

Patients with medically-refractory Parkinson's disease who are planned for MRI-guided DBS surgery under general anesthesia are candidates for this protocol. They will be invited to participate in this study if they decide to have DBS surgery in the intraoperative MRI suite under general anesthesia. Patients who decide to have awake DBS surgery with clinical and electrophysiologic testing will not be eligible. The consenting process will occur in the outpatient clinic setting, and patients will have the opportunity to review the consent document at home with their families. A total of eight patients will be enrolled.

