Secondary: 
• To determine the volume of distribution (Vd) relative to the volume of infusion (Vi) for a convective infusion of autologous CSF into a deep brain nuclear region in humans• To determine the level of effectiveness or symptom response of infusion-enhanced, MRI-guided DBS.	
Methodology: Open-label, single-arm, quantitative study	
Number of subjects (planned): 4	
Diagnosis and main criteria for inclusion: Patients with Parkinson's disease and medically-refractory motor symptoms, who are already planned for MRI-guided DBS electrodes under general anesthesia.	
Investigational intervention: Unilateral infusion of 0.5 ml autologous CSF before DBS electrode insertion with MRI monitoring.	
Other study intervention(s): None	
Criteria for evaluation (i.e. endpoints):	
Efficacy: 
The primary efficacy assessment will be measured with the unmedicated UPDRS, motor subsection (part III) at 6 months in comparison to baseline. Additional efficacy endpoints will include standard, validated assessments of PD before and after DBS. Standard clinical measures of PD will be obtained as per usual clinical protocol at pretreatment baseline and 6 months postoperatively.
	
Safety: 
Safety will be assessed by incidence and severity of AEs, changes in physical examinations, neurological exams and the number of discontinuations due to AEs.
	
Distribution: 
Distribution will be assessed using MRI imaging to calculate the volume of distribution of autologous CSF into the basal ganglia in relation to the volume infused.
	

1. LIST OF ABBREVIATIONS	4
2. BACKGROUND AND RATIONALE	6
2.1. Study Synopsis	6
2.2. Disease Background.....	6
2.3. Case Study	7
2.4. Part 1 Preclinical Animal Studies	8
2.5. Part 2 Preclinical Animal Studies	11
3. STUDY OBJECTIVES.....	12
3.1. Primary Objectives.....	12
3.2. Secondary Objectives	12
4. SUBJECT ELIGIBILITY	13
4.1. Inclusion Criteria	13
4.2. Exclusion Criteria	13
5. TREATMENT PLAN.....	14
5.1. Study Overview.....	14
5.2. Treatment Assignment.....	14
5.3. DBS Surgery and Treatment Administration.....	14
5.4. Concomitant Medications/Treatments	17
5.5. Duration of Study Participation.....	18
5.6. Discontinuation/Withdrawal from Study.....	18
5.7. Subject Status Definitions	18
6. DEVICE INFORMATION	19
7. EVALUATION AND ASSESSMENTS.....	19
7.1. Schedule of Events	19
7.2. Study Assessments	20
7.3. Final Study Visit	22
7.4. Early Termination Visit	22
8. DATA ANALYSIS PLAN.....	22
8.1. Safety	22

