2. BACKGROUND AND RATIONALE

2.1. Study Synopsis

This will be a small feasibility study investigating the safety and feasibility of infusion-enhanced, MRI-guided DBS electrode placement. We intend to enroll four (4) patients, with Parkinson's disease and medically-refractory motor symptoms, who are already planned for MRI-guided DBS electrodes under general anesthesia. Only a single side (nondominant) will be investigated with the research infusion when bilateral DBS electrodes are planned.

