5.5. Duration of Study Participation

Subjects who are enrolled will be followed for six months after their DBS surgery. The Screening and Baseline period is a maximum of 90 days before the surgery and CED infusion. The follow-up period is the first 6 months post-DBS implantation. Follow up clinic visits correspond with routine post DBS clinic follow up and does not include additional visits specific to this research.

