5.7. Subject Status Definitions

Enrolled: All subjects who sign an informed consent will be considered enrolled in the study. All subjects consented on the study will be assigned to the research study in EPIC.

Screen Failure: A subject who is withdrawn or discontinues from the study prior to receiving DBS is considered a screen fail. Screen failures are not considered a study accrual and will be replaced. Note: The IRB defines any individual that has signed an informed consent as an enrollment in this study and so screen failures should be reported to the IRB with enrollment numbers.

On-Study: A subject is considered on-study on the date when the study team has confirmed the subject has met all of the inclusion and none of the exclusion criteria, and the treating physician/surgeon or study PI has signed off on the confirmation.

On-Treatment: A subject is considered on-treatment on the date that the DBS surgery is initiated. A subject who is withdrawn or discontinues from the study after receiving DBS surgery is considered a discontinuation and will not be replaced.

On Follow-up: A subject is considered on follow-up on the date that the DBS surgery is completed.

Off-Study: A subject is considered off-study if they are removed from the study for any of the reasons listed in Section 4.6, or if they have completed all study assessments through follow-up (6 Month follow-up visit).

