8.4. Statistical Considerations and Sample Size

This is an open-label feasibility study of 4 subjects to be recruited from a single center. In order to find 4 eligible subjects suitable for treatment, up to 20 subjects may be consented and screened. For this study, a statistical sample size analysis is not proposed. All those subjects that were consented and then found not meeting study requirements will be considered screen failures.

The Safety and Effectiveness assessment will be descriptive with no statistical endpoints. The results will be examined and analyzed and used as a basis for determining the nature of future studies.

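### Section 4 gives a total enrolment of eight, while the synopsis, Section 2.1 and Section 8.4 plan 4, and nothing in the protocol reconciles the two

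*Combined protocol and SAP*

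**What the plan says.** Section 4 (Subject Eligibility) describes who may be invited and how consent is taken, and ends: "A total of eight patients will be enrolled".

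The other statements of the planned number are:

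- Synopsis: "Number of subjects (planned): 4".
- Section 2.1: "We intend to enroll four (4) patients".
- Section 8.4, first mention: "This is an open-label feasibility study of 4 subjects to be recruited from a single center".
- Section 8.4, second mention, with a consent ceiling: "In order to find 4 eligible subjects suitable for treatment, up to 20 subjects may be consented and screened".

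Two sections bear on the meaning of *enrolled*. Section 5.7 defines it: "All subjects who sign an informed consent will be considered enrolled in the study". Section 5.5 uses it for people who go on to surgery: "Subjects who are enrolled will be followed for six months after their DBS surgery". On replacement, Section 5.7 says of subjects lost before DBS: "Screen failures are not considered a study accrual and will be replaced". Subjects who discontinue after DBS surgery are not replaced. Section 5.1 mentions enrolling patients but gives no number.

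**The concern.** Sections 2.1 and 4 use the same verb with different numbers, and both are current body text of version 5.0. The planned number matters for two reasons.

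First, Section 5.2 plans the infusion for every subject, so the number treated is the number planned for the two procedures that Section 9.5 says differ from standard practice: the lumbar puncture and the intracerebral infusion. Second, the primary safety endpoint in Section 8.1 is the adverse event profile from the procedure to Month 6, and the number treated is its denominator.

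There is also a practical difficulty. Section 10.2 requires the study to be run as the approved protocol describes. If eight means treated, a fifth treated patient fits Section 4 but exceeds Section 8.4, and stopping at four does the reverse.

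**Working it through.** There is no sample-size formula to reproduce, because Section 8.4 states that no sample size analysis is proposed. The check compares the stated counts and tests each way of reconciling them.

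**Inputs**

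| Quantity | Value | Source |
|---|---|---|
| Total enrolled | 8 | Section 4 |
| Planned subjects | 4 | Synopsis; Section 2.1; Section 8.4 (twice) |
| Maximum consented and screened | 20 | Section 8.4 |
| Recruitment rate | about 1 per month | Section 5.1 |
| Study duration | under two years | Section 5.1 |
| Follow-up | 6 months | Section 5.5 |

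**Count of statements.** Four: 1 (synopsis) + 1 (Section 2.1) + 2 (Section 8.4) = 4 statements. Eight: 1 statement (Section 4).

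**Reading A: eight treated.** 8 / 4 = 2, and 8 − 4 = 4 more people planned for the research procedures. This contradicts the synopsis, Section 2.1 and Section 8.4.

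**Reading B: eight consented, using the Section 5.7 definition.** 8 < 20, so the ceiling in Section 8.4 is not broken. But Section 8.4 gives a flexible maximum and Section 4 a fixed total, and no section explains how eight was reached. Applying the same definition to Section 2.1 makes four the number consented. That conflicts with eight, and it sits badly with up to 20 consents to find 4 eligible subjects.

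**Replacement.** Only screen failures are replaced, and they are not counted as accrual. Losses after surgery are not replaced. Replacement therefore cannot turn 4 treated into 8 treated.

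**Timeline.** Accrual months plus follow-up: 4 + 6 = 10 months for four, and 8 + 6 = 14 months for eight. Both are under two years, so the timeline does not decide between them.

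**Illustration of the denominator (not a protocol figure).** If no events of a given kind are seen in n subjects, the exact one-sided 95% upper bound on its rate is 1 − 0.05^(1/n). For n = 4 this is 52.7%; for n = 8 it is 31.2%. Either is wide. The figures show only that the two totals describe safety with different precision.

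**The case against.** The strongest reply is that the harmful reading is the weaker one. Section 5.7 gives the only formal definition of *enrolled*, and it is signing consent. The eight in Section 4 comes directly after the description of the consent process. Section 5.5 is a loose sentence about follow-up and not a second definition. On the consent reading no limit is broken, and the two places where a reader would formally look for the planned number, the synopsis line and the sample-size section, both say 4. Nor would exposure be strictly one for one with subjects, since Section 9.5 abandons the infusion if CSF cannot be obtained or is too bloody.

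Most of this stands. It limits the consequence but does not remove the inconsistency, because Section 2.1 and Section 4 disagree whichever meaning of *enrolled* is applied to both.

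Three stronger inferences should be resisted:

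- **That the protocol plans to treat eight people.** This needs the treated meaning in Section 4, which the Section 5.7 definition does not support.
- **That the ceiling of 20 rules out the consent reading.** A maximum of 20 does not exclude 8.
- **That the trial might fall short of 4 treated if only eight may be consented.** Section 8.4 allows up to 20 consents and Section 5.7 replaces screen failures, so the text does not force a shortfall.

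**Conclusion.** The contradiction is real and should be corrected: eight in one place against 4 in four statements across three places, with nothing that reconciles them. On the treated reading it is a factor of 2, or four more people planned for the research lumbar puncture and infusion. On the consented reading it is an unexplained fixed total that breaks no limit, does not match the ceiling of 20, and conflicts with Section 2.1. The exposure consequence rests wholly on the treated reading.

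The weight of the text favours 4, and eight may be a leftover, but the documents do not say so. No power, type I error or decision rule is at stake, because Section 8 plans descriptive analysis only. The point is worth fixing because the number of people exposed is a basic protocol parameter and the correction is cheap.

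**What to change.** The sponsor confirms two numbers, subjects treated and maximum subjects consented, and states both identically in the synopsis, Section 2.1, Section 4 and Section 8.4. In Section 2.1 and Section 4, *treated* and *consented* replace *enroll* and *enrolled*. The edits then depend on what is intended:

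- **4 treated, at most 20 consented** (as the synopsis and Section 8.4 indicate): replace the Section 4 sentence with one saying that no more than 20 subjects may be consented in order to treat 4.
- **4 treated from eight consented:** reword Section 4 to say so, and also change the 20 in Section 8.4.
- **8 treated:** change the synopsis, Section 2.1 and both mentions in Section 8.4, and put *treated* in Section 4. Confirm whether the ceiling of 20 still holds, since Section 8.4 ties it to finding 4 eligible subjects.

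The first two branches cost a few words and, relative to the 4 in Section 8.4, add no treated subjects. The third means four more treated subjects, with their visits and data. Rewording Section 5.5 to match the definition in Section 5.7 is optional, and Section 5.1 can stand because it carries no number.

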4.1. Inclusion Criteria

1. Men and women, age 30 years and older
2. Subjects with advanced PD who are scheduled for MRI-guided DBS surgery under general anesthesia
3. Subjects who are able and willing to give informed consent and able to attend clinic visits through 6 months
4. The target nucleus, GPi or STN, is visible on MRI so that it can be targeted for the study infusion and then for MRI-guided DBS

4.2. Exclusion Criteria

1. DBS surgery planned in the awake condition with microelectrode recordings and clinical testing
2. Spinal pathology not amenable to lumbar puncture
3. Subjects who have had deep brain stimulation or a prior stereotactic ablation of the basal ganglia
4. Legal incapacity or limited legal capacity as determined by the neuropsychologist
5. Are participating or have participated in another clinical trial in the last 30 days
6. Any illness that in the investigator's opinion preclude participation in this study.
7. Subjects who are prisoners.
8. Women who are pregnant.

9. Subjects who do not speak English. (Questionnaires are validated in English and no other language.)

5. TREATMENT PLAN

5.1. Study Overview

This will be an open-label, single-arm, pilot study investigating the safety and feasibility of infusion-enhanced, MRI-guided DBS electrode placement. We intend to enroll patients, with Parkinson's disease and medically-refractory motor symptoms, who are already planned for MRI-guided DBS electrodes under general anesthesia. The *hypothesis* of the study is that a convective micro-infusion of autologous CSF will enhance the T2-weighted MRI visualization of the targeted nucleus during image-guided DBS surgery for Parkinson's disease. We will record standard clinical measures of PD at baseline and 6 months following DBS surgery. The study will recruit patients at a rate of approximately one a month and will take less than two years to complete.

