2.2. Disease Background

MRI-guided surgery was initially developed in the 1990s for a more precise brain biopsy.^{1,7} Recently, image-guided DBS has been proposed as an alternative to traditional electrophysiologically-guided DBS for medically-refractory Parkinson's disease.^{2,11,13-16,18} MRI-guided DBS can be performed under general anesthesia to avoid the discomfort of awake surgery and the need for prolonged unmedicated states. Clinical outcomes note improved off medication UPDRS motor scores by 60% and 49%, respectively which compares similarly to a recent meta-analysis of 34 studies estimating 52% in PD with STN DBS.⁹

True image-guided surgery adjusts to brain shifting during the procedure and the inherent registration errors that can be associated with image fusion techniques.^{4,8} Contemporary MRI continues to improve so that small stereotactic targets, that previously required intraoperative confirmation of their location with recordings or clinical testing, can now be directly visualized, however there is still room for improvement. McClelland et. al. analyzed electrodes placed using frame-based stereotaxy and microelectrode recording guidance, and found that 40 of 52 electrodes required re-positioning based on electrophysiologic localization.¹⁰ Unfortunately one can't determine whether this is from frame placement error, image fusion, MRI distortion, or stereotactic positioning error.

The assessment of DBS electrode placement relative to a selected target location in stereotactic space is relatively simple, requiring only postoperative imaging to compare with the preoperative plan. Real-time image-guided DBS placement has only recently been realized with compatible skull-mounted frames and high-field MRI. Radial vector error during DBS for PD has been measured at 1.2 ± 0.65 and 0.8 ± 0.4 mm.^{12,16} CT has also been used as a modality to guide asleep DBS surgeries although it is primarily used for image registration and confirmation of the placement as opposed to true image guided, localization during the procedure. Burchiel et al reported similar accuracies, but clinical outcomes are not yet available.²

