3.2. Secondary Objectives

Distribution:

The volume of distribution (Vd) will be determined immediately following the infusion (Vi) with intraoperative 1.5T MRI, T2-weighted sequences. The distribution of the infusion by convective properties in a deep brain human nucleus (GPi or STN) will be determined by calculating the Vd/Vi ratio.

Efficacy:

The primary efficacy assessment will be measured with the unmedicated UPDRS, motor subsection (part III) at 6 months in comparison to baseline. Additional efficacy endpoints will include standard, validated assessments of PD before and after DBS. Standard clinical measures of PD will be obtained as per usual clinical protocol at pretreatment baseline and 6 months postoperatively. These DBS-related assessments include:

- UPDRS in the off and on medication state
- Levodopa medication equivalents (milligrams)
- Neuropsychological assessment
- PDQ-39

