5.3.4. Completion of DBS procedure

The microcatheter is removed, and replaced with the DBS electrode. There is no intraoperative, macrostimulation testing of the DBS electrode as the patient is asleep and electrode position is based on MRI targeting. The electrode is anchored in place, and the wound is closed. For bilateral cases, the contralateral (dominant side) DBS electrode will be inserted as per standard practice without the research infusion protocol.

The second stage of the DBS procedure is then performed on the same day and under the same general anesthetic for placement of the implanted pulse generator. For this, the patient is repositioned in a supine fashion with their head slightly rotated away from the pulse generator site. The ipsilateral scalp, neck, and chest are prepped and draped. The cranial incision is reopened and a small counter incision is made behind the ear. A subcutaneous pocket is made at the clavicular level. The DBS lead extension is tunneled

subcutaneously between the head and chest, such that the appropriate connections can be made from the DBS electrode to the lead extension and then to the pulse generator. Intraoperative lead impedance test is performed to confirm the electrical integrity of the system. The wounds are then copiously irrigated with antibiotic saline and closed. The patient is taken to the recovery area following extubation. Medications are reinstated, and they are observed overnight on a neurosurgical ward for one or two nights. Postoperative MRI is obtained standard of care, and the DBS system is maintained off until programming in the clinic. At the University of Virginia, we routinely perform a postoperative MRI after DBS surgery to assess the final position of the electrode. The imaging is conducted within the conditional limits set forth by the FDA for DBS systems. The final DBS system implanted will be assessed with MRI in one of two scenarios:

DBS systems that are full-body eligible:

- Neurostimulator models 37612 Activa RC, 37603 Activa SC, 37601 Activa PC
- No pocket adaptor can be implanted with the DBS system.
- Fully-implanted leads (ie, leads that are internalized and capped)
- No open or short circuits

DBS systems that are head-only eligible:

- Neurostimulator models 37602 Activa SC, 7428 Kinetra, 7426 Soletra
- Any DBS system that is implanted with a pocket adaptor
- Partially-implanted leads (ie, leads that are externalized)
- No open or short circuits

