8.1. Safety

The PI will evaluate all AE's that occur throughout the study and provide his assessment of the study safety profile as well as his recommendations for the study continuation. All AEs will be communicated to the FDA as part of the annual reporting for this proposed IDE study.

All AEs will be reported and categorized by investigators as definitely, probably, possibly, unlikely, or unrelated to the CSF infusion, and/or Parkinson's disease progression. Standard Code of Federal Regulation definitions for Serious Adverse Events (SAEs) and Unanticipated Adverse Device Effects (UADEs) will be used in assessment of AEs.

Primary safety endpoint for this study is the adverse event profile generated during the CED procedure through Month 6.

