The insertion of the infusion catheter into the brain could also lead to brain injury from intracerebral bleeding or stroke. This risk should not be increased beyond that for routine DBS surgery as the microcatheter will be inserted through a guide cannula that is already positioned for the DBS electrode. Typically, the risk of a hemorrhagic complication from stereotactic insertion of an electrode is ~1%.⁵ Potentially, fewer DBS electrode passes will be required with the improved imaging leading to an overall reduced risk than traditional, awake DBS surgery where multiple microelectrodes are inserted to map the target nucleus.

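### The stated aim is feasibility of infusion-enhanced electrode placement, but no outcome records where the electrode ended up, how many passes it took or whether the infusion was completed

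*Combined protocol and SAP*

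**What the plan says.** **Aim.** Section 2.1: "This will be a small feasibility study investigating the safety and feasibility of infusion-enhanced, MRI-guided DBS electrode placement". Section 5.1 repeats this for the pilot study, "investigating the safety and feasibility of infusion-enhanced, MRI-guided DBS electrode placement", and then gives the hypothesis as better T2-weighted visualization of the target nucleus.

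**Outcomes.** Section 8.1: "Primary safety endpoint for this study is the adverse event profile generated during the CED procedure through Month 6". In Section 3.2, distribution "will be determined by calculating the Vd/Vi ratio". Efficacy is off-medication UPDRS part III at 6 months against baseline (Sections 3.2 and 8.2), with levodopa equivalents and PDQ-39 as secondary endpoints (Section 8.3). Neuropsychology and the examinations are further safety measures.

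**Placement, outside the outcome sections.**
- Section 2.2 describes assessing electrode position against the target as relatively simple, "requiring only postoperative imaging to compare with the preoperative plan", and gives benchmarks: "Radial vector error during DBS for PD has been measured at 1.2 ± 0.65 and 0.8 ± 0.4 mm".
- Section 5.3.4: "we routinely perform a postoperative MRI after DBS surgery to assess the final position of the electrode". The same section calls this scan standard of care.
- Section 5.3.3 mentions a clinical assessment of electrode placement on the 1.5T system.
- Section 9.5, on catheter insertion: "Potentially, fewer DBS electrode passes will be required with the improved imaging".

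**The concern.** A feasibility study of a placement technique would be expected to report, at a minimum, where the electrodes went, how many attempts were needed and whether the added step could be carried out. The protocol gives the rationale, the benchmarks and a routine scan for the first of these, but carries none of the three into an outcome.

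Two things are at stake. First, Sections 8 and 8.4 say the results will help determine the nature of future studies. Procedural data such as pass counts may be unrecoverable if they are not recorded at the time. Second, there is a narrow safety gap. The electrode replaces the microcatheter in tissue that has just been infused. If the tip then lies a millimetre or so from target without symptoms, the primary endpoint need not show it.

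**Working it through.** The plan has no calculation to reproduce. Section 8.4 proposes no sample-size analysis, and no alpha, power or effect size is stated. The check has two parts.

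**1. Does any defined outcome describe placement or completion of the procedure?**

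- *Adverse events (3.1, 8.1, 9.1).* Under Section 9.1 a clinical finding generally counts as an AE if it has symptoms, changes study treatment, needs intervention or a change in concomitant therapy, or is clinically significant in the investigator's judgment. A small silent targeting error can meet none of these.
- *Vd/Vi (3.2).* This measures spread of the infusate, not the electrode. It implies that Vi is known for each infused subject, but it is not a tabulation of infusions attempted, completed or aborted.
- *UPDRS, levodopa equivalents, PDQ-39 (3.2, 8.2, 8.3).* These reflect stimulation, programming and medication titration up to 6 months. In bilateral cases only the nondominant side is infused (5.2), and no side-specific score is planned.
- *MRI (7.1, 7.2.2).* The schedule marks MRI at baseline and at DBS surgery, with no separate postoperative entry. Section 7.2.2 does not describe the postoperative scan.
- *Placement assessment in 5.3.3.* It is not taken up in Sections 3, 7 or 8.
- *Aborted infusion (9.5).* The infusion is abandoned if CSF cannot be obtained or is too bloody. No outcome counts this, and the plan does not say whether such a subject still counts toward the planned number.

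So no outcome covers electrode position, passes, repositionings or infusion completion.

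**2. What could a placement listing show at this size?**

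Inputs: reference means and SDs of 1.2 ± 0.65 mm and 0.8 ± 0.4 mm (Section 2.2); one infused side per subject (5.2); n = 4 (Synopsis, 2.1, 8.4) or n = 8 (Section 4).

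Formula: 95% half-width = t(0.975, n − 1) × SD / √n.

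- n = 4, t = 3.182: 3.182 × 0.65 / 2 = 1.03 mm; 3.182 × 0.4 / 2 = 0.64 mm.
- n = 8, t = 2.365: 2.365 × 0.65 / 2.828 = 0.54 mm; 2.365 × 0.4 / 2.828 = 0.33 mm.

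At n = 4, a mean of 1.2 mm would have an interval of 0.17 to 2.23 mm, and a mean of 0.8 mm an interval of 0.16 to 1.44 mm. The half-widths are 1.03 / 1.2 = 86% and 0.64 / 0.8 = 80% of the means. Radial error cannot be negative and is likely skewed, so these t-intervals are only a rough guide.

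For passes, if 0 of 4 subjects needed more than one, the two-sided 95% exact upper bound is 1 − 0.025^(1/4) = 60%. For 0 of 8 it is 1 − 0.025^(1/8) = 37%.

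**The case against.** **The trial does answer its formal objectives.** Section 3 sets out safety foremost, then distribution and initial effectiveness, and each has an outcome. A reader might infer from the wording of 2.1 and 5.1 that the trial cannot report on its own question. The documents do not support that, because the placement phrase describes the study and is not a listed objective. This part of the objection stands and limits the severity.

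**Radial error would not show that the infusion helps.** The nucleus must already be visible for eligibility (4.1), the trajectory is planned before infusion (5.3.2), and no section describes re-planning afterwards. Tip against plan therefore measures delivery accuracy, not better target choice. This stands. The visualization hypothesis would still have no endpoint, and the reference plan must be stated.

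**The scan does not supply everything.** An MRI of final position cannot count passes or show the volume delivered. The words routine and standard of care also fall short of a guarantee in every subject. Both stand, and they determine the data sources in the fix.

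**Malposition would be noticed.** Placement is assessed during and after surgery, and malposition with clinical consequences could be captured under the definitions in 9.1. This is fair for consequential errors. It does not cover silent ones, and seeing an image is not the same as recording a measurement from it.

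**The claim about passes is mild.** Section 9.5 says only that fewer passes are possible, compared with awake surgery using multiple microelectrodes, which is excluded here. This stands. It is a reason to count passes, not a broken promise.

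**Displacement is not shown.** A reader might take the 0.5 ml maximum and the swine Vd/Vi of 2 to 4.5 (2.4.2), giving 1.0 to 2.25 ml, and by (6V/π)^(1/3) a sphere 12.4 to 16.3 mm across, as evidence that the electrode is displaced. Vd is the region the infusate reaches, not tissue movement, and infusion may stop earlier (5.3.3). No section reports displacement, so the sphere says nothing about placement error.

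**Conclusion.** The gap is real and of minor to moderate weight. Sections 2.1 and 5.1 describe a study of placement feasibility, while Sections 3, 7 and 8 define no placement or procedural-feasibility outcome. A silent targeting error on the infused side could go unrecorded. It is a mismatch between described aim and outcomes in a study declared descriptive, not a sample-size error and not a failure of the formal objectives.

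A placement listing would flag gross error only. The half-width of 0.64 to 1.03 mm at n = 4 assumes that the Section 2.2 SDs carry over to this setting and that each subject contributes one infused side. With n = 8 it would be 0.33 to 0.54 mm. Availability of the scan rests on the statements in Section 5.3.4, because the schedule does not list it separately.

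**What to change.** Add to Sections 3.2 and 8.3 a descriptive listing, one row per electrode, with:

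- (a) radial error of the final tip against the planned target, measured on the postoperative MRI, stating whether the reference is the pre-infusion plan or a plan revised after infusion;
- (b) number of brain passes and repositionings per side, from the operative record;
- (c) infusion attempted, started, completed or aborted, with volume delivered, from the operative and pump records.

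Label each electrode by target and by infused or non-infused side. Show the Section 2.2 benchmarks beside the listing. Treat the non-infused side in bilateral cases as descriptive only. Name the postoperative MRI as a study data source in 7.1 and 7.2.2. State that the listing does not test the visualization hypothesis. Reconcile the planned number of subjects, which is eight in Section 4 and four in the Synopsis, 2.1 and 8.4.

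Cost: one endpoint paragraph, a few case report form fields and a few minutes of measurement per electrode. No added scan or visit and no change to care.
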